**Table 4.a List of Completed Clinical Studies With Brentuximab Vedotin (as of February 2016)**

Study No. Phase	Design	Study Objective	Diagnosis	Dosage (b-v) Frequency Duration (a)	Primary Endpoint	Planned/ Treated/ Analyzed (b)	M:F Median Age (Range)	Study Dates (c)	Sites/ Regions
Clinical Pharmacology Studies									
SGN35-007 Phase 1	Open-label, single-arm	Clinical pharmacology	CD30+ hematologic malignancies	1.8 mg/kg IV q3wk 16 cycles	Duration of ventricular repolarization	48/52/46	48%:52% 34.5 (19-76)	Feb 10-Aug 11	9/US, W Europe
SGN35-008A Phase 1	Open-label, nonrandomized, 3-arm, drug-drug interaction, excretion	Clinical pharmacology	CD30+ hematologic malignancies	1.2 or 1.8 mg/kg IV q3wk 2 cycles	PK parameters	36/56/45	59%:41% 33.5 (16-71)	Dec 09-Jun 10	7/US
SGN35-008B Phase 1	Open-label, nonrandomized, hepatic or renal impairment	Clinical pharmacology	CD30+ hematologic malignancies	1.2 mg/kg IV q3wk 2 cycles	PK parameters	12/17/17	Hepatic 57%:43% 55.0 (22-72)  Renal 50%:50% 56.5 (29-78)	Jan 10-May 12	6/US
C25005 Phase 1	Open-label, 1:1 randomized, single agent or with rifampicin	Metabolite quantification	Relapsed/ refractory classical HL or sALCL	1.8 mg/kg IV q3wk 16 cycles	PK parameters	20/20	≥18 and ≤75	Nov 13-Jun 15	Europe

Footnotes are on last table page.

CONFIDENTIAL

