- Gastrointestinal complications, including events of intestinal obstruction, ileus, enterocolitis, neutropenic colitis, erosion, ulcer, perforation, and hemorrhage, some with fatal outcomes, have been reported in patients treated with brentuximab vedotin. Some cases of gastrointestinal perforations were reported in patients with gastrointestinal involvement of underlying lymphoma. In the event of new or worsening gastrointestinal symptoms, perform a prompt diagnostic evaluation and treat appropriately.
- The pharmacokinetic (PK) of brentuximab vedotin was studied in patients with hepatic or renal impairment. Patients with hepatic impairment (Child-Pugh class A to C) and patients with severe renal impairment (creatinine clearance lower than 30 mL/min) exhibited a trend toward moderate decreases in ADC exposure and increases in MMAE exposure. Therefore, patients with hepatic impairment and/or severe renal impairment at Baseline will not be enrolled in this study. Patients with hepatic or renal impairment during study treatment should be closely monitored for AEs and will be treated based on the local standard of care.
- Co-administration of brentuximab vedotin with ketoconazole, a strong cytochrome P450 (CYP) 3A4 and P-glycoprotein (P-gp) inhibitor, increased the exposure to the antimicrotubule agent MMAE by approximately 73% and did not alter the plasma exposure to brentuximab vedotin. Therefore, co-administration of brentuximab vedotin with strong CYP3A4 and P-gp inhibitors may increase the incidence of neutropenia. If neutropenia develops, refer to [Table 9.a.](#)
- Co-administration of brentuximab vedotin with rifampicin, a strong CYP3A4 inducer, did not alter the plasma exposure to brentuximab vedotin; however, it reduced exposure to MMAE by approximately 31%.
- Co-administration of midazolam, a CYP3A4 substrate, with brentuximab vedotin did not alter the metabolism of midazolam; therefore, brentuximab vedotin is not expected to alter the exposure to medicines that are metabolized by CYP3A4 enzymes.
- The effects of brentuximab vedotin on embryogenesis, reproduction, and spermatogenesis in humans are unknown. In addition, data about the effects of brentuximab vedotin in pregnant women are unavailable. Please see Section [9.5](#) for appropriate precautions triggered by the administration of study medication.

Refer to the brentuximab vedotin IB for details.

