## **8.0 STUDY POPULATION**

### **8.1 Inclusion Criteria**

Each patient must meet all of the following inclusion criteria to be enrolled in the study:

1. Male or female Chinese patients aged 18 years or older at the time of informed consent.
2. Patients must have histologically confirmed CD30+ HL or sALCL. Immunohistochemistry or flow cytometry may be performed on either original diagnostic biopsy material or biopsy of relapsed disease, and pathology reports of CD30+ or their copies should be retained at the site.
3. Patients with CD30+ HL or sALCL who have relapsed from or are refractory to previous treatments.
4. Fluorodeoxyglucose (FDG)-PET positive and measurable disease of at least 1.5 cm in the longest diameter by CT, as assessed by the site.
5. Patients must have an Eastern Cooperative Oncology Group (ECOG) performance status of 0 or 1.
6. Voluntary written consent must be given before performance of any study-related procedure not part of standard medical care, with the understanding that consent may be withdrawn by the patient at any time without prejudice to future medical care.
7. Female patients who:
  - Are postmenopausal for at least 1 year before the screening visit, OR
  - Are surgically sterile, OR
  - If they are of childbearing potential, agree to practice 2 effective methods of contraception, at the same time, from the time of signing the informed consent through 6 months after the last dose of study drug.

Male patients, even if surgically sterilized (ie, status postvasectomy), who:

- Agree to practice effective barrier contraception during the entire study treatment period and through 6 months after the last dose of study drug.

8. Suitable venous access for the study-required blood sampling, including PK sampling.
9. Patients must have the following required screening laboratory data. Patients must not have received recombinant granulocyte-colony stimulating factor (G-CSF) or platelet transfusion within 1 week before the screening hematology assessment.
  - Absolute neutrophil count  $\geq 1500/\mu\text{L}$ .
  - Platelet count  $\geq 75,000/\mu\text{L}$ .
  - Serum bilirubin level  $\leq 1.5$  times the upper limit of the normal range (ULN).
  - Serum creatinine level  $\leq 1.5$  times the ULN.

- Alanine aminotransferase (ALT) and aspartate aminotransferase (AST)  $\leq 2.5$  times the ULN.
- 10. Survival for 3 or more months must be expected.

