## **8.2 Exclusion Criteria**

Patients meeting any of the following exclusion criteria are not to be enrolled in the study:

1. Patients with current diagnosis of primary cutaneous ALCL (patients with other organ involvement who have transformed to sALCL are eligible).
2. Female patients who are lactating and breast-feeding or have a positive serum pregnancy test during the screening period.
3. Patients with any active viral, bacterial, or fungal infection within 2 weeks before the first dose of brentuximab vedotin.
4. Patients with cardiac failure categorized as Class III or IV according to the New York Heart Association criteria, uncontrolled coronary artery disease or uncontrolled arrhythmia despite of appropriate medical therapy, or a history of myocardial infarction within 6 months before the first dose of brentuximab vedotin.
5. Patients with uncontrolled diabetes mellitus.
6. Peripheral neuropathy  $\geq$ Grade 2 (NCI CTCAE version 4.03) [2].
7. Patients with a history of another malignancy that has not been in remission for at least 3 years. The following are exempt from the 3-year limit:
  - Nonmelanoma skin cancer.
  - Curatively treated localized prostate cancer.
  - Cervical carcinoma in situ.
8. Patients with known cerebral/meningeal disease (HL or any other etiology), including signs or symptoms of PML (see Section 9.6.5).
9. Patients with a positive result in the screening test for human immunodeficiency virus (HIV) antibody.
10. Known hepatitis B virus (HBV) surface antigen seropositive or positive hepatitis C virus (HCV) antibody. Note: patients who have positive HBV core antibody can be enrolled but must have an undetectable HBV viral load.
11. Patients with a history of liver fibrosis or cirrhosis and clinical signs and symptoms indicating liver fibrosis or cirrhosis.
12. Patients who have received auto-SCT within 12 weeks before the first dose of brentuximab vedotin.
13. Patients with history of allo-SCT.

14. Patients who have received treatment for malignancies (including radiation, chemotherapy, and hormone therapy) within 4 weeks before the first dose of brentuximab vedotin and patients who have received treatment for malignancies with biologics (including molecular target drug) or radioisotopic therapy within 12 weeks before the first dose of brentuximab vedotin.

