15. Patients who have unresolved toxicity higher than Grade 1 (NCI CTCAE version 4.03) [2] attributed to any prior therapy/procedure (excluding alopecia or non-clinically significant and asymptomatic laboratory abnormalities).
16. Patients who have received systemic corticosteroids at doses greater than the equivalent of 20 mg/day of prednisone within 1 week before the first dose of brentuximab vedotin.
17. Patients who have received other investigational products within 4 weeks before the first dose of brentuximab vedotin.
18. Patients who have received treatment with investigational medical devices within 4 weeks before the first dose of brentuximab vedotin.
19. Patients who have received previous treatment with brentuximab vedotin.
20. Patients with a known hypersensitivity to any excipient contained in the drug formulation.
21. Patients who have any kind of disorder that compromises the ability of the patient to give written informed consent and/or to comply with study procedures.
22. Comorbid systemic illnesses or other severe concurrent disease which, in the judgment of the investigator, would make the patient inappropriate for entry into this study or interfere significantly with the proper assessment of the safety and toxicity of the prescribed regimens.

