#### **10.3.2 Enrollment**

The investigator or investigator's designee will access the IWRS at the screening visit to obtain a unique subject identification number. A subject is considered to be eligible to enter the enrollment visit when the eligibility criteria are met. The subject identification numbers will be used consistently throughout the entire study and must not be changed.

Subjects who do not meet eligibility criteria within the screening period will not be eligible for enrollment. However, subjects may be rescreened at the discretion of the investigator/ subinvestigator, provided that the subject has not been registered as a screen failure. If a subject is being rescreened, the investigator/subinvestigator must obtain additional written informed consent to reconfirm the subject's consent to participate in this study. Subjects may be rescreened only

once. Subjects who will not be rescreened or are determined not eligible after rescreening must be considered screen failures.

The first dose of brentuximab vedotin should be started within 7 days after enrollment. If the first dose cannot be started within 7 days, screening can be repeated after reconsenting.

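### Section 4.1.5 says patients with severe renal or hepatic impairment will not be enrolled, but the eligibility criteria do not fully carry that over

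*Protocol*

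**What the plan says.** Protocol Section 4.1.5 reports that patients with hepatic impairment (Child-Pugh class A to C) and "patients with severe renal impairment (creatinine clearance lower than 30 mL/min") showed a trend toward moderately lower antibody-drug conjugate exposure and higher MMAE exposure. From this it concludes that "patients with hepatic impairment and/or severe renal impairment at Baseline will not be enrolled in this study".

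Eligibility is set out in Sections 8.1 and 8.2 and repeated in the Section 2.0 summary. Section 10.3.2 makes those lists the gate: "A subject is considered to be eligible to enter the enrollment visit when the eligibility criteria are met".

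- **Renal.** Inclusion 9 opens with "Patients must have the following required screening laboratory data" and caps serum creatinine at 1.5 times the ULN. There is no creatinine-clearance limit. Table 10.a lists creatinine but not clearance. Inclusion 1 sets a minimum age of 18 and no maximum.
- **Hepatic.** Inclusion 9 caps bilirubin at 1.5 times and ALT/AST at 2.5 times the ULN. Exclusion 11 reads "Patients with a history of liver fibrosis or cirrhosis and clinical signs and symptoms indicating liver fibrosis or cirrhosis". There is no Child-Pugh criterion.
- **General.** Exclusion 22 covers "Comorbid systemic illnesses or other severe concurrent disease which, in the judgment of the investigator", would make the patient unsuitable. It gives no threshold.

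**The concern.** Section 4.1.5 is phrased as an enrolment rule with a safety reason behind it. A site that works through the numbered criteria can nevertheless pass a patient whom Section 4.1.5 says will not be enrolled. Serum creatinine is an imperfect stand-in for clearance: at a given creatinine, clearance falls with age and with low body weight, and the protocol allows both.

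The stake is the safety of individual patients. Where ketoconazole raised MMAE exposure, Section 4.1.5 warns of more neutropenia. For renal or hepatic impairment it gives only a direction and no size, so the harm to a misclassified patient cannot be quantified from the documents. A secondary stake is one or two atypical profiles in a small pharmacokinetic data set.

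**Working it through.** The plan gives no figure for this point, so there is none to reproduce. The check asks whether the creatinine cap already implies a clearance of at least 30 mL/min.

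**Inputs from the protocol**
- Cap: 1.5 × ULN (inclusion 9). Threshold: 30 mL/min (Section 4.1.5).
- Ages (Table 4.a): medians 31 (HL pivotal study), 41 (Japanese study) and 52 (sALCL pivotal study). Age 76 is the top of the sALCL pivotal range.

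**Assumptions, not in the documents**
- Cockcroft-Gault: CrCl = (140 − age) × kg × f / (72 × creatinine in mg/dL), with f = 0.85 for women and 1 for men.
- ULN 0.9 to 1.1 mg/dL (women) and 1.1 to 1.3 mg/dL (men). The cap is then 1.35 to 1.65 and 1.65 to 1.95 mg/dL.
- Body weights as shown.

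**Main example: 76 years, 50 kg, creatinine at the cap**
- Woman: 64 × 50 × 0.85 = 2720. 2720 / (72 × 1.35) = 28.0; 2720 / (72 × 1.65) = 22.9.
- Man: 64 × 50 = 3200. 3200 / (72 × 1.65) = 26.9; 3200 / (72 × 1.95) = 22.8.

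Both stay below 30 across the whole assumed ULN range.

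**How near the cap must creatinine be?** Clearance equals 30 when creatinine = (140 − age) × kg × f / 2160.
- Woman: 2720 / 2160 = 1.259 mg/dL, which is 1.40 × ULN (ULN 0.9) or 1.14 × ULN (ULN 1.1).
- Man: 3200 / 2160 = 1.481 mg/dL, which is 1.35 × ULN (ULN 1.1) or 1.14 × ULN (ULN 1.3).

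So the gap opens somewhat before the cap is reached.

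**Where the gap closes** (CrCl in mL/min over the assumed ULN range)

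| Case | Woman | Man |
|---|---|---|
| 76 y, 50 kg, at cap | 22.9–28.0 | 22.8–26.9 |
| 76 y, 60 kg, at cap | 27.5–33.6 | 27.4–32.3 |
| 76 y, 70 kg, at cap | 32.1–39.2 | 31.9–37.7 |
| 76 y, 50 kg, at 1.0 × ULN | 34.3–42.0 | 34.2–40.4 |
| 52 y, 50 kg, at cap | 31.5–38.5 | 31.3–37.0 |
| 41 y, 50 kg, at cap | 35.4–43.3 | 35.3–41.7 |
| 31 y, 50 kg, at cap | 39.0–47.7 | 38.8–45.9 |

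**Sensitivity to the ULN.** At 50 kg and the cap, clearance falls below 30 above age 140 − 2160 × creatinine / (50 × f).
- Women: 140 − 2916 / 42.5 = 71.4 years (ULN 0.9), down to 140 − 3564 / 42.5 = 56.1 years (ULN 1.1).
- Men: 140 − 3564 / 50 = 68.7 years (ULN 1.1), down to 140 − 4212 / 50 = 55.8 years (ULN 1.3).

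**Hepatic wording.** This needs reading rather than arithmetic. If the conjunction in exclusion 11 requires both elements, a patient with known cirrhosis, no clinical signs, and bilirubin and transaminases within inclusion 9 is not excluded by it. If it joins two separate groups, that patient is excluded. Exclusion 14 uses the same conjunction to join separate groups, although it repeats its subject to do so and exclusion 11 does not.

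**The case against.** The strongest reply is that the rule is already in the protocol. Appendix B binds investigators to the whole document, Section 9.1 restricts drug to eligible patients, inclusion 9 screens out most renal impairment, and exclusion 22 leaves the rest to judgment. Much of this stands: the cap does cover most of the intent, and a careful investigator who has read Section 4.1.5 would reach the right decision. What remains is that Section 10.3.2 ties enrolment to the criteria, no criterion calls for a clearance, and exclusion 22 supplies no threshold.

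A second reply is that the formula, ULN and weights all come from outside the documents, and the result moves with them. That is true. It limits any claim about how many patients are affected, but not the finding that the cap does not guarantee 30 mL/min.

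Three stronger readings are tempting and not supported:

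- **That the safeguards act too late.** Chemistry A, which includes creatinine, is due within 3 days before the first dose (Section 10.3.10.1), and so is weight (Section 10.3.7). Nor can one say that sites never calculate clearance. The documents only fail to require it.
- **That affected patients would be overdosed relative to tested experience.** Table 4.a lists Study SGN35-008B ("Open-label, nonrandomized, hepatic or renal impairment") at "1.2 mg/kg IV q3wk 2 cycles", against 1.8 mg/kg here. Section 4.1.5 does not name its source study, the 17 treated patients mix hepatic and renal groups, and nothing presents 1.2 mg/kg as a safety ceiling. The comparison shows no harm.
- **That exclusion 11 plainly admits cirrhosis.** It is ambiguous, and Section 4.1.5 supports the stricter reading.

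**Conclusion.** The point holds as a small mismatch between a stated safety exclusion and the criteria meant to apply it. The renal part rests on the text (a 30 mL/min rule in Section 4.1.5, only a creatinine cap in Sections 2.0 and 8) and on the assumed formula, ULN and weights for its size. Older age, low weight and raised creatinine must coincide. The documents do not give the share of such patients, so the expected number among about 30 cannot be estimated. It is probably very few and may be none. The hepatic part is an ambiguity in wording. Neither part affects the response-rate analysis or the sample size.

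**What to change.** - **Sections 2.0 and 8.1, inclusion 9:** add *calculated creatinine clearance ≥30 mL/min (Cockcroft-Gault)*.
- **Sections 2.0 and 8.2, exclusion 11:** reword to *history of, or clinical signs or symptoms indicating, liver fibrosis or cirrhosis*.

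No separate Child-Pugh criterion is proposed. Hepatic impairment without fibrosis or cirrhosis would still rest on the laboratory caps and exclusion 22.

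The cost is protocol wording only. Date of birth and sex (Section 10.3.3), weight (Section 10.3.7) and creatinine (Section 10.3.10.1, Table 10.a) are already obtained before the first dose, so no new test or visit is needed. The downside is that a very few patients may become ineligible.

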## **4.2 Rationale for the Proposed Study**

### **4.2.1 Rationale for Evaluation of HL and sALCL in One Study**

The mechanism and site of action of brentuximab vedotin are the same for both HL and sALCL because brentuximab vedotin exhibits antitumor effects by binding to CD30 on the surface of tumor cells. Additionally, the same tumor response criteria are used for both diseases. The therapeutic strategy is similar for relapsed/refractory HL and sALCL. The phase 2 studies showed that brentuximab vedotin has comparable antitumor effects in patients with relapsed/refractory HL

and sALCL, and there is no marked difference in safety profile. It is therefore appropriate to evaluate brentuximab vedotin in patients with relapsed/refractory HL and sALCL in one study.

#### **4.2.2 Rationale for Dose**

In Study SG035-0001 (first-in-human study), brentuximab vedotin doses from 0.1 to 3.6 mg/kg Q3W were evaluated. No DLT was observed in the cohorts up to 1.2 mg/kg Q3W. DLTs observed in 3 of 12 patients treated at the 2.7 mg/kg dose level included Grade 4 neutropenic fever, Grade 3 prostatitis, Grade 3 hyperglycemia, and 1 case of unrelated acute renal failure. One occurrence of Grade 4 thrombocytopenia qualified as a DLT at the 1.8 mg/kg dose level. The MTD was defined as 1.8 mg/kg administered intravenously (IV) Q3W.

Tumor response (CR+partial remission [PR]) was observed at doses above 1.2 mg/kg Q3W. The subsequent clinical studies have used a dose of 1.8 mg/kg Q3W as the optimal dose.

In the phase 1 part of Study TB-BC010088 (Japan phase 1/2 study), brentuximab vedotin was evaluated at dose levels of 1.2 and 1.8 mg/kg administered Q3W to determine the phase 2 dose. No DLT was observed in the phase 1 part of this study, and the 1.8 mg/kg dose level was selected for the phase 2 part. The resulting tumor response at 1.8 mg/kg by the IRF was 67% (95% CI; 29.9, 92.5) for relapsed/refractory HL and 100% (95% CI; 54.9, 100.0) for relapsed/refractory sALCL. Tumor sizes were reduced in all subjects in the phase 2 part for whom measurements were available, and the safety profile was manageable.

The same brentuximab vedotin dosing schedule of 1.8 mg/kg Q3W was used in the Study SGN35-005 (global phase 3 study). The safety findings from this study were similar to those from pivotal phase 2 studies SG035-0003 and SG035-0004. At the time of the interim OS analysis, data are immature and limited by the small number of events observed within a relatively short follow-up period; however, the difference in median PFS in this study per IRF between the brentuximab vedotin arm and placebo arm was statistically significant by the stratified log rank test ( $p=0.001$ ).

Based on these data, it is appropriate to use 1.8 mg/kg Q3W as the brentuximab vedotin dose in Chinese patients. This dose has been approved in 62 countries for patients with relapsed or refractory CD30-positive HL and sALCL.

## **5.0 STUDY OBJECTIVES**

### **5.1 Primary Objective**

The primary objective is to evaluate the efficacy and the safety of brentuximab vedotin in Chinese patients with relapsed/refractory CD30+ HL or sALCL.

### **5.2 Secondary Objective**

The secondary objective is to evaluate the PK and immunogenicity of brentuximab vedotin in Chinese patients with relapsed/refractory CD30+ HL or sALCL.

## **6.0 STUDY ENDPOINTS**

### **6.1 Primary Endpoints**

The primary endpoints are:

- ORR.
- Safety: AEs, assessments of clinical laboratory values, and vital sign measurements.

### **6.2 Secondary Endpoints**

The secondary endpoints are:

- CR rate.
- DOR.
- PFS.
- OS.
- B symptom resolution rate.
- Maximum observed plasma concentration ( $C_{\max}$ ).
- Time to reach  $C_{\max}$  ( $t_{\max}$ ).
- Area under the plasma concentration-time curve from time 0 to infinity ( $AUC_{0-\infty}$ ).
- Presence of antitherapeutic antibodies (ATA) and neutralizing antitherapeutic antibodies (nATA) to brentuximab vedotin.

## **7.0 STUDY DESIGN**

### **7.1 Overview of Study Design**

This is a single-arm, open-label, multicenter, phase 2 study designed to evaluate the efficacy, safety, and PK of brentuximab vedotin as a single agent in Chinese patients with relapsed/refractory CD30+ HL or sALCL. Brentuximab vedotin will be administered as a single, 1.8 mg/kg IV infusion on Day 1 of each 3-week cycle.

Patients will receive a maximum of 16 cycles if they do not meet the criteria for removal from the study. Patients will be assessed for overall response using the Revised Response Criteria for Malignant Lymphoma [1]. Dedicated computed tomography (CT) scans (neck, chest, abdomen, and pelvis) will be performed at Baseline and at Cycles 2, 4, 7, 10, 13, and 16, and positron emission tomography (PET) scans will be performed at Baseline and at Cycles 4 and 7. No additional PET scanning is required beyond Cycle 7 unless clinically indicated. B symptoms will be assessed at Baseline and on Day 1 of each cycle.

Patients may continue on study treatment until the sooner of disease progression, unacceptable toxicity, or completion of 16 cycles. Patients, including those who discontinue study treatment for any reason other than withdrawal of consent, will have safety follow-up assessments through 30 days after the last dose of study drug (end of treatment [EOT]). Patients who discontinue study treatment with stable disease (SD) or better will be followed for PFS until disease progression, death, withdrawal of consent, or initiation of a new treatment, whichever occurs first. A CT scan will be performed every 12 weeks for the first 12 months and at 18 months after EOT. Patients will be followed for OS every 12 weeks until death, withdrawal of consent, or study closure, whichever occurs first. All patients will have the opportunity to be followed for 18 months after EOT. The study will be closed when all patients enrolled have completed the required follow-up.

Toxicity will be evaluated according to the National Cancer Institute Common Terminology Criteria for Adverse Events (NCI CTCAE), version 4.03, effective 14 June 2010 [2]. Laboratory values, vital signs, and electrocardiograms (ECGs) will be obtained to evaluate the safety and tolerability of brentuximab vedotin. Serial blood samples for determination of the serum/plasma concentration and immunogenicity of brentuximab vedotin will be obtained at prespecified time points as described in Table B in [Appendix A](#).

